Figure 4: Fibroblastic foci in UIP/IPF demonstrate expression of dityrosine, a marker of oxidative protein cross-linking reactions. IPF tissue sections were stained with a mouse monoclonal antibody (1:50 dilution) against dityrosine by immunohistochemistry (TruBlue). Control staining was with biotinylated secondary IgG antibody. Intense staining of dityrosine was identified primarily in fibroblastic foci around alveolar spaces (AS). Arrows point to dityrosine-expressing (blue staining) fibroblastic foci in UIP/IPF.

These findings have been interpreted as evidence the myo-Fbs within these foci actively secrete H_2O_2 , which then induces the formation of oxidatively- modified proteins by a *o,o'*-dityrosine-dependent mechanism.

1.3.7 Plasma levels of *o,o'*-dityrosine Are Increased in IPF Patients:

Tyrosine residues in proteins are susceptible to covalent oxidative modifications, including the formation of *o,o'*-dityrosine (31) (**Fig. 5**). Since these covalent modifications are stable, protein tyrosine (P-Tyr) modifications in circulating plasma may serve as a potential biomarker of oxidative injury.

[figure not shown]
[figure not shown]

Figure 5: Chemical structure and extracted ion chromatograms measures of soluble *o,o'*-dityrosine. (A) Chemical structure of *o,o'*-dityrosine. 'R' represents the α -carbon linking the peptide bonds within a protein molecule. (B) Chromatogram from plasma of a subject with IPF. The protein hydrolysate from plasma samples were separated by reverse phase HPLC and subjected to ESI/MS. Extracted ion chromatograms were derived from the MRM transitions for *o,o'*-dityrosine. The ratio of ion currents for each amino acid compared with the internal standard (depicted by *) was utilized to quantify the levels of *o,o'*-dityrosine; note co-elution of authentic oxidized amino acid to the corresponding isotopically labeled internal standard.

We found plasma concentrations of *o,o'*-dityrosine were much greater among IPF patients (8.51 ± 0.94 $\mu\text{mol/mole}$ tyrosine) compared to healthy controls (0.47 ± 0.07 $\mu\text{mol/mole}$ tyrosine) (**Fig. 6**). The respective values for individuals within these two groups were almost completely separated and, overall, there was an 18-fold intergroup difference.

Figure 6: *o,o'*-dityrosine is increased in plasma of IPF patients.

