The effects of GKT137831 on plasma levels of ROS-associated biomarkers was tested in mice with and without bleomycin-induced lung injury. Bleomycin treatment again resulted in a striking increase in plasma levels of o,o'-dityrosine (Figure 8), analogous to findings in humans with IPF (see Section 1.3.7). Most importantly, GKT137831 therapy resulted in >5-fold reductions of plasma o,o'-dityrosine among the bleomycin-treated animals with pulmonary fibrosis. This GKT137831 treatment effect on o,o'-dityrosine was of a greater magnitude and more significant than reductions of other ROS biomarkers (3'-nitrotyrosine and 3'-chlorotyrosine) (data not shown).

[figure not shown]

Figure 8. GKT831 administration causes *in vivo* reductions of mechanistic ROS biomarker o,o'-dityrosine. Aged female B6 mice were treated with intra-tracheal bleomycin or saline, and then GKT831 (40 mg/kg) was administered daily by gavage. While bleomycin treatment resulted in large increases in circulating o,o'-dityrosine, levels of this metabolite were normalized by GKT831 therapy. N=6 in GKT831-treated groups, # denotes p = 0.012).

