2.8 DATA ANALYSES AND POWER ANALYSES

2.8.1. Data analyses: Baseline demographic and clinical data of participants will be summarized using means (with standard deviations) and medians (with inter-quartile ranges) for continuous variables, and counts and percentages for discrete variables, stratified by treatment group. Differences between groups (to examine the randomization effectiveness), will be assessed by t-tests, or by Fisher's exact test for discrete data. Analyses will follow intention to treat principles, with the last observed outcome over all time points being used as the primary measure for a given variable. Multiple imputation will be used based on subject characteristics to assess the obvious issues, with last observations carried forward in these analyses. Trajectories over time, for a given patient and outcome measure, will be displayed via line graphs, and assessments conducted using generalized linear models on the repeated time points. Comparisons between the treatment arms of circulating o,o'-dityrosine levels at various time points will be made using these repeated measures techniques. Transformations of these tests may be needed, such as velocities, if many individuals are unable to complete the entire protocol.

2.8.2. Power analyses: The sample size of 60 for this clinical trial (equally divided between experimental and placebo arms) is based on exposing a minimum number of patients to risks of experimental therapy, while still obtaining useful information. We previously found that o,o'-dityrosine levels ($\mu\text{mol/mol}$ tyrosine) in IPF patients ($n = 32$) were 8.51, with a standard deviation (SD) of 5.30, compared to mean and SD of 0.47 ± 0.45 in normal controls (15). Assuming o,o'-dityrosine levels are reduced in the experimental arm subjects by 50% of the difference between untreated IPF and normals (e.g., to $4.02 \mu\text{mol/mol}$ tyrosine), with a SD of 5.3 we will be able to reject the null hypothesis that the population means of the experimental and control groups are equal with probability (power) 0.82, using an unpaired, two-way t-test. The Type I error probability associated with this test of this null hypothesis is 0.05. The 50% reduction is well within ranges in which ROS and fibrosis markers are decreased by GKT137831 in other models (Sec. 1.3.9., and 8-11).

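### Dityrosine is powered on raw means with the SD held at 5.3 after the mean is roughly halved, and the primary analysis names neither a scale nor baseline adjustment

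*Combined protocol and SAP*

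**What the plan says.** The power calculation is in Section 2.8.2:

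- **Size:** "The sample size of 60 for this clinical trial (equally divided between experimental and placebo arms").
- **Test:** it is done "using an unpaired, two-way t-test". On alpha, the plan states: "The Type I error probability associated with this test of this null hypothesis is 0.05".
- **Effect and SD:** treatment is assumed to remove half the gap between IPF patients (mean 8.51, SD 5.30) and healthy controls, "compared to mean and SD of 0.47 ± 0.45 in normal controls". One SD is then used for both arms: "with a SD of 5.3 we will be able to reject the null hypothesis". The power given for this comparison is 0.82.

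The Synopsis defines the primary endpoint as the change in plasma dityrosine between baseline and Week 24. Section 2.8.1 says arms will be compared with generalised linear models fitted to the repeated measurements. It gives no link, error distribution or scale, and no baseline covariate. The only transformation it mentions is to velocities, in case many patients have incomplete follow-up.

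The background sections describe differences in dityrosine as ratios. Section 1.3.7 says "overall, there was an 18-fold intergroup difference" between patients and controls. Section 1.3.9 says "GKT137831 therapy resulted in >5-fold reductions of plasma o,o'-dityrosine among the bleomycin-treated animals".

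**The concern.** A treated mean of 4.49 with SD 5.3 describes a non-negative quantity whose SD exceeds its mean. The two groups for which the protocol has data suggest that the SD falls with the mean. The planning SD therefore has little support in the protocol's own figures, and the 0.82 may misdescribe the planned test.

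The second gap is in the analysis. With no scale and no baseline handling fixed, raw or log, level or change, adjusted or unadjusted would all fit the text. In a 60-patient trial these choices can move power by tens of percentage points, and as written they could be made after the data are seen.

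**Working it through.** **1. Reproduce 0.82.** Half the gap is 0.5 × (8.51 − 0.47) = 4.02, so the treated mean is 8.51 − 4.02 = 4.49. A two-sided, two-sample t-test (noncentral t) with 30 per arm, difference 4.02, SD 5.3 and alpha 0.05 has power 0.823. The text prints 4.02 as the level reached. Read that way the difference is 4.49 and power is 0.897, so the stated 0.82 treats 4.02 as the difference. The calculation is on raw means with one SD for both arms.

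**2. Check the SDs.** Section 1.3.7 gives standard errors of 0.94 (n = 32) and 0.07 (n = 42). 0.94 × √32 = 5.32 and 0.07 × √42 = 0.454, in agreement with Section 2.8.2.

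**3. How the SD moves with the mean.**
- Raw SD ratio: 5.30/0.45 = 11.8.
- Coefficients of variation (CV): 5.30/8.51 = 0.62 and 0.45/0.47 = 0.96.
- Log SDs if lognormal, √ln(1 + CV²): 0.573 and 0.807, a ratio of 1.41. This is much nearer to constant than the raw SDs, but not equal.
- A normal model with SD 5.3 puts Φ(−4.49/5.3) = 20% of treated values below zero, and Φ(−8.51/5.3) = 5% of untreated IPF values.

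**4. Power if the SD shrinks with the mean.** At the IPF CV the treated SD is 0.623 × 4.49 = 2.80. The pooled SD is √((5.3² + 2.80²)/2) = 4.24, and raw-scale power is 0.951 by the same formula.

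**5. Log-scale power, conditional on lognormal data.** The log difference is ln(8.51/4.49) = 0.639. With 30 per arm, power is 0.989 at log SD 0.573 and 0.855 at 0.807.

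**6. Simulation of the candidate analyses.** There were 20,000 trials per row, 30 per arm, with treated Week-24 values multiplied by 4.49/8.51 = 0.53. Both arms have the same CV, and both visits have mean 8.51 before treatment. The baseline to Week-24 correlation of 0.5 (on the underlying normal scale) is an assumption. ANCOVA means Week-24 value on arm plus baseline.

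| Data, CV | Week-24 raw t | Week-24 log t | Raw change t | Raw ANCOVA | Log ANCOVA |
|---|---|---|---|---|---|
| Lognormal, 0.62 | 0.97 | 0.99 | 0.86 | 0.99 | >0.99 |
| Lognormal, 0.96 | 0.74 | 0.86 | 0.53 | 0.82 | 0.93 |
| Gamma, 0.62 | 0.97 | 0.94 | 0.87 | 0.99 | 0.98 |
| Gamma, 0.96 | 0.69 | 0.54 | 0.50 | 0.78 | 0.64 |

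CV 0.96 is a stress case: at mean 8.51 it implies an SD of 0.957 × 8.51 = 8.1, against the documented 5.30.

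At correlation 0.7, both ANCOVAs again beat the raw change score in all four rows. For a smaller assumed ratio of 0.7 (CV 0.62, correlation 0.5), raw change, raw ANCOVA and log ANCOVA give 0.49, 0.69 and 0.78 under lognormal data, and 0.48, 0.68 and 0.62 under gamma data. Type I error was 0.04 to 0.05 for every method.

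**The case against.** Several objections stand and limit the point.

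- **The plan does not commit to a raw analysis.** The t-test appears only in the power section, and the named model class includes log-link and gamma models. The gap is an unstated scale, not a wrong one. Likewise, the raw change score is one reading of the Synopsis endpoint, used here as a benchmark.
- **No treated-patient SD is given.** The two SDs come from untreated patients and healthy controls. A mixture of responders and non-responders could keep the SD wide while the mean falls. The figures make a constant SD doubtful; they do not refute it.
- **Lognormality cannot be shown.** Only means and SDs were available, and the CV is not constant. A reader might infer that the log scale fits the data and gains power. Under lognormal data at the documented IPF CV the log alone adds only 1 to 2 points. Under gamma data it loses.
- **The ratio evidence is indirect.** One figure compares disease with health and the other is from mice. The trial's own effect assumption is an absolute difference, which a difference in means answers directly.
- **The correlation may be higher than assumed.** Section 2.8.2 also claims 0.8 power for a within-arm fall of 1.4 in 30 patients. That implies an SD of change near 2.65, and so a correlation of 1 − 2.65²/(2 × 5.3²) = 0.875 if both SDs are 5.3. A change-score comparison of 4.02 with SD 2.65 then has power above 0.999, so the choice would matter only for smaller effects. The protocol gives no source for that SD.

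None of this answers the two gaps: the support for the constant SD, and the unstated scale and baseline handling.

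**Conclusion.** The point holds in limited form. The SD of 5.3 at a mean of 4.49 is poorly supported by the protocol's own figures, and the primary analysis leaves scale and baseline adjustment open.

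Two stronger readings are not supported. The trial is not shown to be underpowered: 0.82 is conservative if the SD shrinks with the mean at the IPF CV (0.95 on the raw scale). The raw test is not shown to be invalid either. The 20% below zero concerns individual values under a normal model, and the test's Type I error held under skewed data.

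What is at stake is power for the same patients and samples. With correlation 0.5, adjusting for baseline on the raw scale adds about 12 to 29 points over a raw change score. Under lognormal data the log then adds from less than 1 point (CV 0.62) to about 12 (CV 0.96). Under gamma data it takes away 1 to 14. These sizes rest on the assumed correlation, a proportional effect and the assumed distributions. The direction of the gain from baseline adjustment was the same in every scenario run.

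**What to change.** Before unblinding:

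1. Specify the primary between-arm comparison at Week 24 as baseline-adjusted, with baseline dityrosine as covariate.
2. Look at the baseline distribution pooled over both arms, blinded, against a criterion written down first. If it supports the log scale, analyse log dityrosine with log baseline. Report the geometric mean ratio with 95% CI, with the baseline-adjusted raw difference as sensitivity analysis. If it does not, make the baseline-adjusted raw difference primary.
3. Fix a rule for values below the assay limit.
4. Show power under both SD assumptions: 0.82 with constant SD 5.3, and 0.95 with proportional SD on the raw scale. Add log-scale power of about 0.99 to 0.855 for log SD 0.57 to 0.81, labelled as conditional on lognormal data. State whether 4.02 is the difference or the level reached.

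The cost is plan wording and one blinded look at baseline values. No patients, visits or assays are added. If the log scale is chosen, the effect is reported as a ratio, which is less direct for an absolute hypothesis; the raw sensitivity analysis covers that.

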	
15) Systemically administered potent CYP3A4 inhibitors or inducers are prohibited during the 24-week treatment period.
 
Inhibitors include: boceprevir, cobicistat, conivaptan, ritonavir, itraconazole, ketoconazole, telaprevir, troleandomycin, voriconazole, clarithromycin, diltiazem, idelalisib, nefazodone, nelfinavir.
 
Inducers include carbamazepine, enzalutamide, mitotane, phenytoin, rifampin.
 
See also: https://www.fda.gov/drugs/drug-interactions-labeling/drug-development-and-drug-interactions-table-substrates-inhibitors-and-inducers#table3-2

Study Endpoints:	
 • Primary efficacy endpoint: The primary efficacy endpoint is change in plasma o,o'-dityrosine, as determined by mass spectroscopy, from baseline to Week 24. • Secondary efficacy endpoints: Secondary efficacy endpoints are: (a) collagen degradation products, (e.g., C1M), measured in sera by ELISA; (b) forced vital capacity (FVC); and (c) six-minute walk distance (6MWD) comparing baseline to values at 24 weeks.
	
 • Safety: Adverse events (AEs) that occur anytime during the duration of the trial. Clinical laboratory evaluations will occur at Screening, baseline/Day 1 and Weeks 6, 12, 18, and 24. Urinalysis will be performed at Screening, baseline/Day 1 and Weeks 6, 12, 18, and 24. Pulse rate, SBP and DBP are recorded at Screening, baseline/Day 1 and Weeks 6, 12, 18, and 24. Body weight at Screening, baseline/Day 1 and Weeks 6, 12, 18, and 24. 12-lead ECG at Screening, baseline/Day 1 and Weeks 6, 12, 18, and 24.
	
 • Pharmacokinetics (PK): Plasma concentrations of GKT137831 and its main phase 1 metabolite, GKT138184. The plasma concentrations will be subjected to population PK analysis to estimate population PK parameters such as clearance and volume of distribution and associated inter-individual variability (IIV), and to determine predictors of IIV. PK-PD analysis will be carried out using the primary endpoint and selected secondary endpoints in order to explore any potential PK-PD relationships.

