2.4 RANDOMIZATION

A randomization list (1:1 experimental arm to controls), stratified by gender (IPF progression is gender-dependent), and use vs. non-use of antifibrotics (i.e., either pirfenidone or nintedanib) at enrollment, will be generated by the Data Coordinating Center (DCC) in advance. Given our "n", additional stratifications could result in imbalances with no subjects in certain cells.

The subject selection and randomizations, and specimen acquisitions for primary and secondary endpoint determinations (to follow), will also enable provision of blood specimens for the translational studies in other associated translational studies. Subject selections here will also identify a population from whom potential participants in additional studies (e.g., experimental bronchoscopies) can be approached and recruited. However, experimental bronchoscopies are optional and distinct from this clinical trial and will require an additional, separate IRB approval and signed consent. The subjects randomized to this GKT137831 clinical trial may elect to not participate with experimental bronchoscopy or other experimental procedures, and they will not be pressured to do so.

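### The primary dityrosine analysis names no baseline or stratification term, and the 0.82 power applies only to an unadjusted comparison of levels

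*Combined protocol and SAP*

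**What the plan says.** The synopsis (Study Endpoints) gives the primary endpoint as change in plasma o,o'-dityrosine, "as determined by mass spectroscopy, from baseline to Week 24". Section 2.7.1 words it differently: treatment effects on plasma levels, measured before treatment and every six weeks.

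Section 2.4 has the randomisation list "stratified by gender (IPF progression is gender-dependent), and use vs. non-use of antifibrotics" at enrolment.

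Section 2.8.1 takes the last observed outcome as the primary measure for each variable. It compares dityrosine levels between arms with generalized linear models on the repeated time points. No covariate is named for any of these models.

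Section 2.8.2 starts from IPF levels that "were 8.51, with a standard deviation (SD) of 5.30" (n = 32), "compared to mean and SD of 0.47 ± 0.45 in normal controls (15"). It assumes that treatment removes half of the gap and concludes that the hypothesis of equal means is rejected when they are "equal with probability (power) 0.82, using an unpaired, two-way t-test". Its next paragraph makes a separate claim for the 30 active-arm subjects alone: 0.8 power, by a paired test, for a fall from baseline of 1.4.

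**The concern.** Three parts of the plan do not line up. The synopsis endpoint is a change. The analysis and the power calculation concern attained levels. The factors that govern randomisation appear in no stated analysis.

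The pretreatment value is usually the strongest available predictor of a later value of the same biomarker, and it is already being collected. With 60 patients, leaving it unspecified gives up precision. It also leaves the choice between raw level, change score and adjusted analysis open until after the data are in. Ignoring the stratification factors can make the standard error too large, so that intervals are wider than they need be.

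The power statement is also hard to use. It rests on the spread between patients at one time, whereas the adjacent paired claim rests on an unstated and much smaller spread of change within patients.

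**Working it through.** **Inputs.** From Section 2.8.2: 60 patients, 30 per arm; IPF mean 8.51, SD 5.30; control mean 0.47; two-sided alpha 0.05 (two-way is read as two-sided). The SEM of 0.94 with n = 32 in Section 1.3.7 gives 0.94 × √32 = 5.32, which agrees with the SD. The assumed difference is 0.5 × (8.51 − 0.47) = 4.02. Section 2.8.2 prints 4.02 as the level reached, but the stated power matches 4.02 as the difference.

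**The plan's figure.** Noncentrality = 4.02 / (5.3 × √(2/30)) = 2.94 on 58 df, giving power 0.823. The stated 0.82 reproduces as an unpaired t-test of levels. A one-sided test would give 0.896.

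**What the paired claim implies.** Solving a two-sided paired t-test (n = 30, fall 1.4, power 0.8) for the SD of change gives about 2.65. If the SD is 5.3 at both times, SD of change = 5.3 × √(2(1 − r)), so r = 1 − 2.65² / (2 × 5.3²) = about 0.875.

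**Power by method.** Under randomisation the expected between-arm difference is 4.02 for either level or change. The plan states no r, so the r values below are assumptions, except 0.875, which is the implied value. Simple change uses the SD above on 58 df. The adjusted analysis uses SD = 5.3 × √(1 − r²) on 55 df (baseline plus two stratification terms).

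| r | SD of change | Power, simple change | Adjusted SD | Power, adjusted |
|---|---|---|---|---|
| 0 | 7.50 | 0.53 | 5.30 | 0.82 |
| 0.2 | 6.70 | 0.63 | 5.19 | 0.84 |
| 0.3 | 6.27 | 0.69 | 5.06 | 0.86 |
| 0.5 | 5.30 | 0.82 | 4.59 | 0.92 |
| 0.7 | 4.11 | 0.96 | 3.78 | 0.98 |
| 0.875 | 2.65 | >0.999 | 2.57 | >0.99 |

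An unadjusted comparison of levels stays at 0.82 whatever r is.

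**Finite-sample cost.** The adjusted column allows for lost degrees of freedom but not for chance covariate imbalance. Allowing for both at r = 0, power is about 0.817 with baseline alone and about 0.80 with three covariates of no prognostic value, against 0.823 unadjusted. The loss is therefore about two points at most.

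**Stratification factors, hypothetical.** Suppose the strata explain a share R² of the dityrosine variance and are almost perfectly balanced. The unadjusted test then runs at a true level of 2 × P(Z > 1.96/√(1 − R²)): 0.039 for R² = 0.10 and 0.028 for R² = 0.20. The documents support neither R² value.

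**The case against.** The strongest reply is that the plan agrees with itself where it matters. Section 2.8.1 analyses levels, Section 2.7.1 words the endpoint as levels, and Section 2.8.2 powers a comparison of levels. Because of randomisation, that comparison validly tests the same treatment effect as a comparison of changes. This stands. The mismatch is with the synopsis wording and with the paired claim, and the 0.82 is not an error.

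A reader might infer from the simple-change column that true power is only 0.53 to 0.69. The documents do not support that. Those figures belong to an unadjusted change-score t-test, which Section 2.8.1 does not propose, and they need r of 0.3 or less. The only information on r in the documents is the paired claim, which points to about 0.875. At r between 0 and 0.3 that claim would itself have power of only about 0.17 to 0.22. The plan gives no source for the smaller SD, however, so r is not established either way.

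A reader might also infer that adjustment is ruled out. It is not: the text is silent, and the pretreatment value could enter the repeated-measures model as one of the responses.

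Nor do the stratification figures show an inflated type I error. Any effect is conservative. The rationale in Section 2.4 concerns disease progression and not dityrosine, and it describes no blocking that would guarantee balance.

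**Conclusion.** The point holds as an inexpensive improvement to the analysis and a clarification of the power statement. The plan specifies no baseline, sex or antifibrotic term, words the primary endpoint in two ways, and uses two unreconciled assumptions about variability (5.3 for levels, about 2.65 implied for change).

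On the plan's own SD and effect, baseline adjustment moves power from 0.82 to 0.86 at r = 0.3, 0.92 at r = 0.5 and 0.98 at r = 0.7, with a possible loss of about two points if no covariate is prognostic. These figures assume equal SDs at both times, 30 evaluable patients per arm and a single Week 24 comparison. An unadjusted change score would fall below 0.82 only if r is under 0.5. No change in sample size follows from this point.

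**What to change.** **Section 2.8.1.** Make the primary analysis the Week 24 between-arm contrast from a repeated-measures model with treatment, visit, treatment-by-visit, baseline dityrosine (with visit interaction), sex and antifibrotic use at enrolment. Use the same baseline-plus-strata form for C1M. For FVC and 6MWD, which are measured only at baseline and Week 24, use ANCOVA at Week 24 with baseline and the two strata.

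**Synopsis and Section 2.7.1.** Word the primary endpoint the same way in both places.

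**Section 2.8.2.** State that 0.82 is for an unadjusted comparison of levels. Give adjusted-model power over a range of r that includes 0.875, and state the SD of change behind the paired claim and where it comes from.

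**Cost.** Changes of wording, to be made before unblinding. Baseline values and both strata are already collected. The Week 24 contrast gives up about three degrees of freedom.
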